### Cohort Sampling

This is a retrospective cohort study with risk-set sampling for exposure status of convalescent plasma using EHRs in the Baylor Scott & White Health (BSWH) healthcare delivery system. In brief, patients who received convalescent plasma will be matched to a similar population who did not receive convalescent plasma around the same time ( $\pm 2$  days) of transfusion across sites. The administration date of convalescent plasma for the treated population and the matched date for the untreated population are thereafter referred as the index date. The matching scheme for risk-set sampling is defined in step-by-

step points in the following paragraph. The follow-up for the matched cohort will start from the index date and continue until the end of the observation period. The observation period for this study is defined as at least 28 days from the index date. In other words, the index date must be at least 28 days prior to the date of data pull to allow for adequate follow-up and minimize selection bias from informative censoring due to death or discharge for palliative care. An unexposed patient at the index date could receive convalescent plasma during the follow-up and the follow-up will be censored at the administration date of convalescent plasma (Figure 1).

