#### Comparative Analyses

A Kaplan-Meier curve will be plotted using the propensity score matched cohorts. To control for measured confounding, patients will be sampled in risk sets with replacement and propensity score matched. Distribution of covariates between exposure groups before and after propensity score matching will be assessed to evaluate the balance of baseline covariates and potential residual confounding. Absolute standardized differences, the differences in means or proportions divided by the pooled standard deviation, will be computed for each covariate to check its distribution balance within exposure groups. Covariates with an absolute standard difference greater than 0.1 will be further controlled in the analyses by including specific variables in the Cox model.

The adjusted incidence rates of death in the first 7, 14, 21, and 28 days after the index date will be estimated for the exposed and unexposed groups using the propensity score-matched cohort.

For the primary outcome (28-day in-hospital mortality), a Cox proportional hazards regression will estimate hazards ratios (HRs) and 95% confidence intervals (CIs) using the propensity score-matched cohort. Patients will be followed from the index date until the earliest of the following: 1) death, 2) discharge alive, 3) day 28 since the index date, or 4) the date of unexposed patients who were administered COVID-19 convalescent plasma. Patients discharged alive will be censored at the discharge date. The proportional hazards assumption will be evaluated using Schoenfeld residuals test and visual inspection of log-log plots.

For the secondary outcome of discharge alive, we will not censor the follow-up at the date of in-hospital death but will censor at day 28 to account for this worst possible outcome and to account for the competing risk of in-hospital death. In other words, patients will be followed from the index date until the earliest of the following: 1) discharge alive, 2) day 28 since the index date, or 3) the date of unexposed patients who were administered COVID-19 convalescent plasma.

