### Sensitivity Analyses

- 1) To assess the COVID-19 cohort definition of hospital admission within ±14 days of laboratory confirmed COVID-19 diagnosis, we will further restrict the source population to those who were admitted into affiliated BSWH hospitals within ±7 days of laboratory confirmed COVID-19 diagnosis. This is because COVID-19 could progress quickly and patients could also transfer to hospitals outside of the network of BSWH with a large time window around COVID-19

confirmation resulting in potential residual confounding by severity and survivor bias by prior treatment

- 2) Instead of ending the observation period at 28 days since the index date, we will continue follow-up until the end of the study period, unless an outcome event occurs earlier. Patients will be followed from the index date until the earliest of the following: 1) death, 2) discharge alive, 3) the end of the study period, or 4) the date of unexposed patients who were administrated COVID-19 convalescent plasma.
- 3) Given that mortality data after hospital discharge is limited and that patients could be discharged for palliative care due to disease worsening, the outcome “discharge alive” will be considered a competing risk for 28-day in-hospital mortality. To account for competing risk of in-hospital death and discharge alive, sub-distribution hazard ratios will be estimated from the Fine-Gray model. Cumulative incidence function will be estimated by modeling the cause-specific hazard function of all causes.

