**VI. LIMITATIONS**

Unmeasured confounding

Given that patients were not randomly assigned to receive convalescent plasma, confounding by indication may not be fully accounted for using the available data elements in EHRs. Missing data and misclassification for covariates may result in residual confounding and biased risk estimates. For example, the convalescent plasma exposed group may appear to have a more favorable clinical outcome compared to the unexposed group, because the unexposed group had more severe disease to start with, and the two groups were not comparable at the index date. Alternatively, the exposed group may appear to have no favorable clinical outcomes or even worse outcomes, because patients in this group started with more severe disease at the index date.

Although risk-set sampling and propensity score matching are used to control measured confounding, EHRs are not able to fully capture all important prognostic factors related to outcomes of interest. To evaluate the possible impact of unmeasured confounding, we will consider exploring some of the methods listed below if feasible.

- Quantitative bias analyses
- Negative outcome controls
- E-values 
- Instrumental variables

Informative censoring

Treatment switches or hospital transfers during follow-up may be related to worsening of COVID-19. To evaluate this potential selection bias, we will use an intent-to-treat (ITT) analysis, whereby treatment switches will not censor the follow-up and instead fixed duration of follow-up will be used. Reasons for and where patients were transferred will be assessed according to exposure groups.

Effect modification by antibody titer

This observational study does not impose the inclusion criterion of seronegative for SARS-CoV-2 because testing antibody titers before administering convalescent plasma is not the present routine clinical practice at BSWH. Hence, individual antibody titers/humoral immunity in patients is not accounted for. The neutralizing capacity of convalescent plasma received by patients is not tested nor captured in the EHRs. In addition, the effective level of neutralizing titers inpatients who have received passive antibody therapies is also unknown. If a limited or no association between convalescent plasma and the clinical outcomes are observed, the results may not be interpreted as a true “no effect” of convalescent plasma due to the uncertainty of the titer values.

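### Fine-Gray sensitivity analysis for 28-day mortality: censoring weights should be estimated by exposure group, because only unexposed patients can be censored before day 28

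*Protocol*

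**What the plan says.** In Section IV, Sensitivity Analyses, item 3, live discharge "will be considered a competing risk for 28-day in-hospital mortality", and "sub-distribution hazard ratios will be estimated from the Fine-Gray model". The item also plans cumulative incidence functions built from cause-specific hazards. It says nothing about how the Fine-Gray censoring weights are estimated, and it neither repeats nor lifts the crossover rule.

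That rule is in two other places. Cohort Sampling (Section III) says: "An unexposed patient at the index date could receive convalescent plasma during the follow-up and the follow-up will be censored at the administration date". Comparative Analyses (Section IV) lists among the ends of follow-up for the primary outcome "the date of unexposed patients who were administered COVID-19 convalescent plasma". Both apply to unexposed patients only.

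Cohort Sampling also requires that "the index date must be at least 28 days prior to the date of data pull", so nobody is censored administratively before day 28. Exposed patients therefore have no planned censoring in that window.

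Section VI (Informative censoring) accepts that "Treatment switches or hospital transfers during follow-up may be related to worsening of COVID-19" and plans an intent-to-treat analysis "whereby treatment switches will not censor the follow-up and instead fixed duration of follow-up will be used". That analysis is not tied to the Fine-Gray model.

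**The concern.** The Fine-Gray model keeps patients who have had the competing event, here live discharge, in the risk set. Their weight falls over time to reflect the chance that they would have been censored had they not been discharged. In its ordinary form the model takes that chance from one censoring curve for everyone, which is valid only if censoring does not depend on the covariates in the model. Here, before day 28, censoring depends entirely on exposure, the covariate of interest.

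A pooled curve is then wrong in both groups. Discharged plasma patients are weighted down although none of them could have been censored, so the exposed risk set is too small and the exposed death hazard too high. Discharged unexposed patients are not weighted down enough, so the unexposed hazard is too low. The ratio moves up even if crossover is unrelated to prognosis.

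Item 3 is a check on a primary Cox model that censors at discharge. An upward shift produced by the weights could be misread as an effect of discharge, or could make a real benefit look smaller.

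**Working it through.** **1. The plan's own related figure.** The Protocol gives no crossover rate and no figure for the Fine-Gray analysis. Table 1 (Section V) is the nearest anchor. Take control mortality 0.25, 80% power, two-sided 0.05, k unexposed per exposed patient, and read the table's relative risk RR as a 28-day risk ratio:

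- HR = ln(1 − 0.25·RR) / ln(0.75)
- deaths = (1.960 + 0.842)² · (k + HR)² / [k·(1 − HR)²]
- N = deaths / [(0.25·RR + k·0.25)/(k + 1)]

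Solving for RR at N = 2,000 and k = 4 gives 0.727, printed as 0.73. All 16 rows agree to two decimals. The 25% mortality carries forward.

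**2. Inputs for the bias.** From the Protocol: 25% dead by day 28, matching up to 1:4, crossover censoring in the unexposed only. Assumed: 65% discharged alive and 10% still in hospital at day 28, constant hazards, crossover independent of prognosis. *Crossover* means the proportion of unexposed patients who receive plasma before death or discharge within 28 days.

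- Total hazard: −ln(0.10)/28 = 0.0822 per day
- Death: 0.0822 × 0.25/0.90 = 0.0228. Discharge: 0.0822 × 0.65/0.90 = 0.0594

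**3. The weights.** A patient discharged at day s has weight G(t)/G(s) at a later day t, where G is the probability of remaining uncensored. Take 20% crossover spread over 28 days, 1:4 matching and no plasma effect. The crossover hazard c solves c/(c + 0.0822) × [1 − exp(−28(c + 0.0822))] = 0.20, which gives c = 0.02205 per day. At day 14:

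- unexposed: G = exp(−0.02205 × 14) = 0.734
- exposed: G = 1
- pooled: G = (4 × 0.734 + 1)/5 = 0.787

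A patient discharged soon after the index date gets weight 0.787 in either group. The correct weights are 1 (exposed) and 0.734 (unexposed).

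**4. Effect on the subdistribution hazard ratio.** Solving the large-sample Fine-Gray estimating equation numerically, with no plasma effect and 1:4 matching:

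| Crossover | Pooled weights, spread over 28 days | Pooled weights, all in days 0-5 | Weights by group |
|---|---|---|---|
| 5% | 1.015 | 1.007 | 1.000 |
| 10% | 1.031 | 1.015 | 1.000 |
| 20% | 1.067 | 1.031 | 1.000 |
| 30% | 1.107 | 1.049 | 1.000 |
| 50% | 1.209 | 1.094 | 1.000 |

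The matching ratio hardly matters. With a cause-specific hazard ratio of 0.7, the value without crossover is 0.716. At 10, 20 and 30% crossover, pooled weights give 0.738, 0.764 and 0.793 (spread) or 0.726, 0.737 and 0.750 (days 0-5). Weights by group give 0.715 to 0.716.

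**5. Against sampling error.** For the Table 1 row with 400 exposed and 1,600 unexposed, 25% mortality means 100 and 400 deaths, so the standard error of the log ratio is roughly √(1/100 + 1/400) = 0.112, ignoring deaths lost to crossover. With spread crossover, the null shift is ln(1.031)/0.112 = 0.27 standard errors at 10%, ln(1.067)/0.112 = 0.58 at 20% and ln(1.107)/0.112 = 0.91 at 30%.

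**6. If crossover depends on prognosis.** A simulation with no plasma effect (200,000 exposed, 1:2, about 18-29% crossover) gave:

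| Who crosses over | Pooled | By group | No crossover censoring |
|---|---|---|---|
| Sicker patients | 1.14 to 1.43 | 1.10 to 1.30 | 1.00 to 1.01 |
| Healthier patients | 0.89 to 1.01 | 0.85 to 0.92 | 0.99 to 1.00 |

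**The case against.** The strongest reply is that the Protocol never prescribes pooled weights. It names the model, and it names SAS and R without a procedure or option. Weight estimation is often left to a separate SAP, which is not among the documents. This stands in part: pooled weights are an inference from the unqualified model name. But the ordinary form of the named method, combined with the plan's own one-sided censoring rule, gives a shifted estimate, so the point is more than a missing detail.

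Second, item 3 has another output, cumulative incidence from cause-specific hazards, that treats discharge as competing without these weights. This stands. A reader might infer that the study's only competing-risk check on mortality is compromised; it is not. The two outputs of item 3 could, however, disagree for a reason unrelated to discharge.

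Third, Section VI already plans an analysis without crossover censoring, in which the asymmetry disappears. That is true, but the Protocol does not link it to the Fine-Gray model. If linked, it is part of the remedy.

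Fourth, the direction is not certain and the remedy is incomplete. This stands where crossover depends on prognosis. When healthier patients cross over, the pooled ratio can fall below 1, and weights by group can lie farther from the null than pooled ones. When sicker patients cross over, which is the case Section VI has in mind, the two biases have the same sign.

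Fifth, the shift is small at low crossover, and the affected estimate is one sensitivity analysis. Both stand.

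**Conclusion.** The point holds conditionally. If item 3 is fitted with one pooled censoring curve, and crossover is unrelated to prognosis, the subdistribution hazard ratio is shifted against plasma by about 1-3% at 5-10% crossover, 3-7% at 20% and 5-11% at 30%. The lower figure at 20% and 30% is for crossover in the first five days, the upper for crossover spread over 28 days. These sizes rest on an assumed crossover rate and timing, 65% discharged alive and constant hazards; only the 25% mortality comes from the Protocol.

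A reader might infer that the planned analysis is biased against plasma whatever happens. The documents do not support that: they fix neither the weights nor the crossover rate, and the net direction is open once crossover depends on prognosis. Nor is the primary result affected, because the Cox model uses no such weights. The change is worth making because the shift is avoidable at almost no cost, but it is not critical to the study's main conclusion.

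**What to change.** In Sensitivity Analyses, item 3:

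- State that the censoring distribution for the Fine-Gray weights is estimated separately in the exposed and unexposed groups.
- Also fit the Fine-Gray model under the Section VI intent-to-treat rule. With no crossover censoring and at least 28 days of observation, no weighting is needed to day 28. This fit compares plasma at the index date with no plasma at that date, so later plasma in the unexposed group can dilute a real effect; report it beside the weighted fit, not instead of it.
- Report the proportion of unexposed patients who crossed over and the timing, so that readers can judge how much the weights could matter.

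The cost is one model option or a short weighting step, one extra model fit and possibly a slightly larger standard error. Weights by group do not deal with crossover driven by prognosis; the intent-to-treat fit is the planned analysis that avoids that censoring.

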### HIV+ patients

Among patients with HIV+ from the source population, we will explore distributions of risk-set match factors (Section III. Study Design) according to exposure to convalescent plasma. The crude incidence rates of death and discharge alive in the first 7, 14, 21, and 28 days after the index date will be estimated for the exposed and unexposed groups.

All statistical analyses will be conducted with SAS 9.4 and R 3.5.1.

## V. SAMPLE SIZE

To achieve 80% power for relative risk ratios of at least 0.7 for all-cause mortality, a sample size calculation was performed based on an assumed background survival rate of 0.75 over 28 days among hospitalized COVID-19 patients receiving usual care in the RCT for dexamethasone and a convalescent plasma to comparator ratio of 1:1, 1:2, 1:3 and 1:4. Using a two-sided log-rank test, estimated sample sizes are listed in **Table 1**.

The feasibility assessment found that the maximum number of patients who received convalescent plasma was 729 during April 1, 2020 to August 6, 2020, we greyed out rows in **Table 1** with required sample size surpassing the maximum and deemed those inapplicable.

**Table 1. Sample size estimates given background survival rate of hospitalized COVID-19 patients and 80% of power at a two-sided 0.05 significance level**

Total sample size	Sample size for convalescent plasma	Match ratio	Relative risk ratio
1,000	500	1:1	0.71
1,500	750	1:1	0.76
2,000	1,000	1:1	0.79
2,500	1,250	1:1	0.81
1,000	333	1:2	0.68
1,500	500	1:2	0.74
2,000	666	1:2	0.77
2,500	833	1:2	0.80

Total sample size	Sample size for convalescent plasma	Match ratio	Relative risk ratio
1,000	248	1:3	0.65
1,500	372	1:3	0.71
2,000	496	1:3	0.75
2,500	620	1:3	0.78
1,000	200	1:4	0.61
1,500	300	1:4	0.68
2,000	400	1:4	0.73
2,500	500	1:4	0.76

**VI. LIMITATIONS**

Unmeasured confounding

Given that patients were not randomly assigned to receive convalescent plasma, confounding by indication may not be fully accounted for using the available data elements in EHRs. Missing data and misclassification for covariates may result in residual confounding and biased risk estimates. For example, the convalescent plasma exposed group may appear to have a more favorable clinical outcome compared to the unexposed group, because the unexposed group had more severe disease to start with, and the two groups were not comparable at the index date. Alternatively, the exposed group may appear to have no favorable clinical outcomes or even worse outcomes, because patients in this group started with more severe disease at the index date.

Although risk-set sampling and propensity score matching are used to control measured confounding, EHRs are not able to fully capture all important prognostic factors related to outcomes of interest. To evaluate the possible impact of unmeasured confounding, we will consider exploring some of the methods listed below if feasible.

- Quantitative bias analyses
- Negative outcome controls
- E-values 
- Instrumental variables

Informative censoring

Treatment switches or hospital transfers during follow-up may be related to worsening of COVID-19. To evaluate this potential selection bias, we will use an intent-to-treat (ITT) analysis, whereby treatment switches will not censor the follow-up and instead fixed duration of follow-up will be used. Reasons for and where patients were transferred will be assessed according to exposure groups.

Effect modification by antibody titer

This observational study does not impose the inclusion criterion of seronegative for SARS-CoV-2 because testing antibody titers before administering convalescent plasma is not the present routine clinical practice at BSWH. Hence, individual antibody titers/humoral immunity in patients is not accounted for. The neutralizing capacity of convalescent plasma received by patients is not tested nor captured in the EHRs. In addition, the effective level of neutralizing titers inpatients who have received passive antibody therapies is also unknown. If a limited or no association between convalescent plasma and the clinical outcomes are observed, the results may not be interpreted as a true “no effect” of convalescent plasma due to the uncertainty of the titer values.

### Generalizability

All studies estimate effects in a specific study population. Clinical practice and coding in EHR systems differ across healthcare systems. Therefore, results from this study may not hold true in other populations.

### Other

The theoretical concern of antibody-mediated enhancement of infection, where antibodies to SARS-CoV-2 could enhance infection to another viral strain, is not assessed in this study.

## **VII. INSTITUTIONAL REVIEW BOARD APPROVAL AND OTHER AUTHORIZATIONS**

This study has been reviewed and approved by the Institutional Review Boards (IRB) of BSWH.

**IX. APPENDICES**

## Appendix 1. International Society of Blood Transfusion (ISBT)-128 codes for convalescent plasma

- E9743 Apheresis CONVALESCENT PLASMA | NS/XX/<=-25C | COVID-19
- E9744 Apheresis CONVALESCENT PLASMA | NS/XX/<=-25C | Methylene blue-treated | COVID-19
- E9745 Apheresis CONVALESCENT PLASMA | NS/XX/<=-25C | Psoralen-treated | COVID-19
- E9746 Apheresis CONVALESCENT PLASMA | NS/XX/<=-25C | Riboflavin-treated | COVID-19
- E9747 Apheresis CONVALESCENT PLASMA | ACD-A/XX/<=-18C | COVID-19
- E9748 Apheresis CONVALESCENT PLASMA | NS/XX/Frozen | COVID-19
- E9749 CONVALESCENT PLASMA | NS/XX/Frozen | COVID-19
- E9750 Liquid Apheresis CONVALESCENT PLASMA | NS/XX/refg | COVID-19
- E9751 Liquid CONVALESCENT PLASMA | NS/XX/refg | COVID-19
- E9752 Thawed Apheresis CONVALESCENT PLASMA | ACD-A/XX/refg | COVID-19
- E9764 Thawed Apheresis CONVALESCENT PLASMA | ACD-A/XX/refg | 3rd container | COVID-19
- E9763 Thawed Apheresis CONVALESCENT PLASMA | ACD-A/XX/refg | 2nd container | COVID-19
- E9754 Apheresis CONVALESCENT PLASMA | ACD-A/XX/<=-18C | 1st container | COVID-19
- E9762 Thawed Apheresis CONVALESCENT PLASMA | ACD-A/XX/refg | 1st container | COVID-19
- E9765 Thawed Apheresis CONVALESCENT PLASMA | ACD-A/XX/refg | 4th container | COVID-19

## Appendix 2. Baseline covariates

- Age (continuous)
- Race and ethnicity
- Site
- Comorbidities in the past 12 months including the index date unless specified
  - History of cancer
    - Hematopoietic
    - Solid tumor excluding non-melanoma skin cancer
    - Non-melanoma skin cancer
  - Cardiovascular conditions
    - Stroke
    - Thrombotic or thromboembolic complications including stroke, myocardial infarction, venous thromboembolism, deep vein thrombosis, and pulmonary embolism
    - Hypertension
    - Heart failure
    - Cardiac arrhythmias including ventricular tachycardia, ventricular fibrillation, atrial arrhythmia, and cardiac arrest
  - Chronic respiratory disease
    - Chronic obstructive pulmonary disease
    - Asthma
  - Diabetes
  - Chronic kidney disease 1-4
  - Chronic kidney disease 5 or end-stage renal disease
  - Chronic liver disease
  - History of organ transplantation
  - HIV
  
  - Obesity at admission
  - Sickle cell disease
- Pregnancy status (yes, no) from index date to study completion
- Comedications from hospital admission to the index date
  - Antiviral drugs
    - Remdesivir
    - Lopinavir/Ritonavir
    - Other HIV protease inhibitors.
  - Hydroxychloroquine/Chloroquine
  - Azithromycin
  - Glucocorticoid/Steroids
    - Dexamethasone
    - Prednisone
    - Hydrocortisone
    - Methylprednisolone
  - Anti-platelet agents
  - IL-6 inhibitor/antagonist
    - Tocilizumab
    - Sarilumab

- Siltuximab
  - ACE-Inhibitors (ACEi)/Angiotensin Receptor Blockers (ARBs)
  - Anti-thrombotic drugs
- Disease severity based on level of oxygenation support (Appendix 3) 4-12 hours prior to index
- Vital signs closest to the index date
  - Respiratory rate
  - Heart rate
  - Systolic blood pressure
  - Temperature
- Laboratory results closest to index date
  - Creatinine,
  - D-dimer
  - Cardiac troponin (TnI or TnT)
  - Absolute lymphocyte count
  - Ferritin
  - C-reactive protein

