The propensity score is defined as the probability of a patient receiving convalescent plasma conditioned on their observed baseline covariates. Baseline is defined as the period prior to and including the index date. Baseline covariates for the propensity score modeling is listed below and further defined in Appendix 2. To account for confounding by baseline covariates described below, a logistic regression will be fitted to estimate the probability of receiving convalescent plasma. In the event of low frequency of certain covariates, that may cause model convergence problem, such covariates will be removed from the propensity score model. Covariates that are strongly related to convalescent plasma transfusion but only weakly related to the primary outcome will not be included in the propensity model to preserve precision of the estimates. Exposed and unexposed patients will be matched according to propensity score with nearest neighbor caliper matching algorithm without replacement with a match ratio up to 1:4 based on the power calculation (Section V. Sample Size). Propensity density plots pre- and post-matching will be evaluated for overlapping areas.

- Age (continuous)
- Race and ethnicity
- Hospital site
- Comorbidities
- Concomitant medications
- Oxygen requirements as a proxy for disease severity (Appendix 3) 4-12 hours prior to the index date

- Laboratory results: creatinine, D-dimer, troponin, absolute lymphocyte count, ferritin, C-reactive protein
- Vital signs: Respiratory rate (min), Heart rate (min), Systolic BP (mmHg), Temperature (°C)

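### The matching variables and propensity score include no dementia, pre-admission residence or other frailty measure, so confounding by selection for active treatment may remain and the balance check cannot show it

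*Protocol*

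**What the plan says.** Four places in the protocol fix what is controlled.

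- **Risk-set matching (Cohort Sampling, step 3):** calendar date within 2 days, age within 5 years, sex, and days from admission to index.
- **Propensity score (Cohort Sampling, step 4):** age, race and ethnicity, site, comorbidities, medications, oxygen requirement, six laboratory tests and four vital signs. The text adds: "Baseline covariates for the propensity score modeling is listed below and further defined in Appendix 2".
- **Appendix 2:** the comorbidity block opens with "Comorbidities in the past 12 months including the index date unless specified". It names cancer, cardiovascular conditions, COPD and asthma, diabetes, kidney and liver disease, transplantation, HIV, obesity and sickle cell disease. Dementia, facility residence, functional status, a frailty score and limits on care do not appear.
- **Comparative Analyses:** a covariate whose absolute standardized difference exceeds 0.1 after matching is added to the Cox model.

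Limitations concedes that "confounding by indication may not be fully accounted for using the available data elements in EHRs" and that "EHRs are not able to fully capture all important prognostic factors related to outcomes of interest". It does not name frailty. For unmeasured confounding it lists quantitative bias analysis, negative outcome controls, E-values and instrumental variables, with the commitment "we will consider exploring some of the methods listed below if feasible".

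**The concern.** Among patients of the same age, oxygen requirement and laboratory values, frailty plausibly predicts both in-hospital death and who is offered an additional treatment. A variable related to both belongs in the score. The protocol's own exclusion rule removes only covariates tied to transfusion but weakly tied to the primary outcome, so it would not keep frailty out.

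The protocol knows of a palliative pathway, since "patients could be discharged for palliative care due to disease worsening". It uses this only for follow-up and competing risk. No baseline covariate records who was a candidate for escalation.

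The primary hazard ratio is at stake. If recipients are the less frail group, the error runs in the direction of the effect the study is sized to detect. The safeguard against residual imbalance works only on tabulated covariates. Limitations presents the problem as one of available data, yet comorbidities are already being collected for the score, and a dementia diagnosis is the same kind of item.

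**Working it through.** **Benchmark from the plan.** Table 1 gives a detectable ratio of 0.76 for 500 recipients at 1:4 (total 2,500), 80% power, two-sided 0.05, background survival 0.75. Using Freedman's log-rank formula with the ratio read as a ratio of 28-day mortality:

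- S1 = 1 − 0.25 × 0.76 = 0.81
- h = ln(0.81)/ln(0.75) = 0.732
- d = 500 × 0.19 + 2,000 × 0.25 = 595 deaths; r = 500/2,000 = 0.25
- √(d·r)·(1 − h)/(1 + r·h) = 2.758; power = Φ(2.758 − 1.960) = 0.79

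Table 1 therefore reproduces, and 0.76 is a fair yardstick. This point does not affect the table.

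**Bias at a true null.** Let p1 and p0 be frailty prevalence in recipients and comparators after matching, and R the mortality ratio for frailty. The documents give none of these, so all values are assumptions.

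Apparent ratio = [1 + p1(R − 1)] / [1 + p0(R − 1)]

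| p1 vs p0 | R = 1.5 | R = 2.0 |
|---|---|---|
| 5% vs 8% | 1.025/1.040 = 0.986 | 1.05/1.08 = 0.972 |
| 5% vs 12% | 1.025/1.060 = 0.967 | 1.05/1.12 = 0.938 |
| 8% vs 15% | 1.040/1.075 = 0.967 | 1.08/1.15 = 0.939 |
| 10% vs 10% | 1.000 | 1.000 |
| 20% vs 10% (reversed) | 1.10/1.05 = 1.048 | 1.20/1.10 = 1.091 |

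This is a risk-ratio formula. Converted to a hazard ratio with the plan's survival of 0.75, the most extreme value is ln(1 − 0.25 × 0.9375)/ln(0.75) = 0.93, so the approximation matters little.

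Against the yardstick, the largest shift is (1 − 0.9375)/(1 − 0.76) = 0.26, about a quarter of the detectable effect. The smallest is 0.014/0.24 = 0.06.

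**Chance of a false significant benefit** (nominal 2.5%) = Φ(−1.96 − ln(b)/se), with b the biased ratio, se = 1/√[d·a(1 − a)] and a the recipients' share. The first figure is for 1,000 patients at 1:1, the second for 2,500 at 1:4.

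- b = 0.97: 4.3% and 4.9%
- b = 0.95: 6.0% and 7.4%
- b = 0.94: 7.0% and 8.9%

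**Would the 0.1 rule have reacted?** Standardized difference = |p1 − p0| / √{[p1(1 − p1) + p0(1 − p0)]/2}:

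- 5% vs 8%: 0.03/0.246 = 0.12
- 5% vs 12%: 0.07/0.277 = 0.25
- 8% vs 15%: 0.07/0.317 = 0.22

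All three exceed 0.1. Had the variable been tabulated, each imbalance would have led to adjustment in the Cox model. As it is not, none would be seen.

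**How much would be needed to explain a full effect?** E-value = R′ + √[R′(R′ − 1)] with R′ = 1/ratio. For 0.76 it is 1.96 and for 0.70 it is 2.21. A single confounder would need both associations at least that strong. With a low-prevalence marker that is necessary but not sufficient, as the modest shifts in the table show.

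**The case against.** A reader might infer that recipients are compared with frailer patients and that plasma will therefore look protective when it does nothing. The documents do not support that. They give no frailty prevalence, no mortality ratio and no relation between frailty and plasma use in this system. Limitations says that confounding may run either way: "the convalescent plasma exposed group may appear to have a more favorable clinical outcome compared to the unexposed group", or alternatively "the exposed group may appear to have no favorable clinical outcomes or even worse outcomes". The direction is a plausible assumption only.

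The plan also controls more than age. Remdesivir, steroids and IL-6 inhibitors given between admission and index bear on selection for active treatment. Stroke, heart failure, kidney failure, COPD and cancer plausibly correlate with frailty, and site and days from admission are handled too. These should shrink any imbalance, so the 3 to 7 points assumed to remain after matching may be too many. The endpoint is in-hospital death with censoring at live discharge, so deaths after palliative discharge are not events. A mortality ratio for all deaths could overstate R here. Both arguments stand, and both make the likely shift smaller.

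It could be said that Limitations already answers the point. It does so in part: it names suitable methods but commits to none of them. Nor is this a matter left to a separate analysis plan, since the protocol fixes the covariate set and its use itself.

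A reader might also want chronic coronary disease added on the same grounds. It is not a frailty marker, and nothing here gives a size for its omission, so it is not part of this point.

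**Conclusion.** The omission is real: no matching variable or propensity-score covariate measures dementia, residence before admission or frailty. The listed proxies are partial, so confounding by selection for active treatment may remain. Under assumed residual imbalances of 3 to 7 points toward frailer comparators and mortality ratios of 1.5 to 2.0, a null effect would appear as about 0.94 to 0.99. Balance gives 1.00, and frailer recipients give a ratio above 1.

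The shift of about 1% to 6% would not by itself produce the effects in Table 1, but at the upper end it could more than double the nominal 2.5% chance of a false benefit. The plan contains no false statement or contradiction here. This is an inexpensive improvement to a covariate list that leaves the balance rule blind to one plausible confounder.

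**What to change.** 1. Add dementia, by diagnosis code, to Appendix 2, and so to the propensity score and the balance table.
2. Where admission source is recorded, add residence before admission (home versus nursing or long-term-care facility) in the same way. Report its completeness by hospital.
3. In Limitations, name frailty as a potential unmeasured confounder. Replace the conditional wording with a commitment to report the E-value or the quantitative bias analysis already listed, showing imbalance in both directions.

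The cost is a short extra code list and one field for patients already being extracted. The documents do not show that admission source is usable across all 25 hospitals, and the data-element table in Appendix 4 is still empty. If the field proves too incomplete, items 1 and 3 still stand.
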